## **6.4. Windowing Conventions**

Allowed time window for each visit will be performed as mentioned in “Schedule of Activities”, section 1.3 of protocol. Intervals between study visits are included in [Table C](#) (Co-Ad group) and [Table D](#) (Control group) and window conventions are included in [Table E](#) (Co-Ad group and Control group).

CCI

**Table C: Intervals between Study Visits (Co-Ad Group)**

Interval	Planned visit interval	Allowed interval range*
Visit 1 (Day 1) → Remote Contact (Day 8)*	8 days	-
Visit 1 (Day 1) → Visit 2 (Day 31)	30 days	30-42 days
Visit 1 (Day 1) → Visit 3 (Day 61)	60 days	60-84 days
Visit 3 (Day 61) → Visit 4 (Day 91)	30 days	30-42 days
Visit 3 → Phone contact	180 days	180-210 days

Note: Participants may not be eligible for the HZ/su and RSV Per Protocol Set (PPS) if the visits happen beyond this interval. Intervals between visits and phone contact do not affect HZ/su and RSV PPS eligibility.

\*Day 8 Remote Contact is applicable to the sentinel group only.

**Table D: Intervals between Study Visits (Control Group)**

Interval	Planned visit interval	Allowed interval range*
Visit 1 (Day 1) → Remote Contact (Day 8)*	8 days	-
Visit 1 (Day 1) → Visit 2 (Day 31)	30 days	30-42 days
Visit 2 (Day 31) → Visit 3 (Day 61)	30 days	30-42 days
Visit 3 (Day 61) → Visit 4 (Day 91)	30 days	30-42 days
Visit 3 → Phone contact	180 days	180-210 days

Note: Participants may not be eligible for the HZ/su and RSV Per Protocol Set (PPS) if the visits happen beyond this interval. Intervals between visits and phone contact do not affect HZ/su and RSV PPS eligibility.

\*Day 8 Remote Contact is applicable to the sentinel group only.

**Table E: Window convention (Co-Ad Group and Control Group)**

Assigned Study Day	Visit label as per protocol	Visit assigned
Day 1	Visit 1	Visit 1 (Day 1)
Day 31 (Day 1 + 30 to 42 days)	Visit 2	Visit 2 (Day 31)
Day 61 (Day 1 + 60 to 84 days)	Visit 3	Visit 3 (Day 61)
Day 91 (Day 1 + 90 to 126 days)	Visit 4	Visit 4 (Day 91)

## 6.5. Statistical Tests

The default significant level will be (5%), CIs will be 95% and all tests will be two-sided, unless otherwise specified in the description of the analyses.

95% CI for proportion will be based on exact Clopper-Pearson CI [18].

95% CI for group difference in proportion will be based on Miettinen and Nurminen CI [18].

The least square point estimate and its 2-sided 95% CI will be derived from an ANCOVA model on log10 transformed concentration/titer. Covariate and factor included in the model are described in [7.1](#).

## 6.6. Common Calculations

GMT/GMC:

Prior to any statistical analysis that assumes normally distributed observations, antibody concentrations or titers will be log10-transformed. GMT/GMC calculations are performed by taking the inverse logarithm of the mean of the log titer or concentration transformations.

The GMT/GMC will be calculated using the following formula:

$$10^{\frac{\sum_{i=1}^n \log_{10}(t_i)}{n}}$$

where  $t_i$  = concentrations or titers for each antibody,  $n$  = number of antibodies examined. Non-quantifiable antibody titers or concentrations will be converted as described in [Table G](#) for the purpose of GMT/GMC calculation. Cut-off values are defined by the laboratory before the analysis.

MG1 (mean geometric increase): The geometric mean of the within participant ratios of the post-dose concentration/titer over the pre-dose concentration/titer.

VRR for anti-gE post-second dose is defined as the percentage of participants who have at least:

A 4-fold increase post-vaccination anti-gE antibody concentration as compared to (over) the pre-vaccination anti-gE antibody concentration, for participants who are seropositive at pre-vaccination, or,

A 4-fold increase post-vaccination anti-gE antibody concentration as compared to (over) the anti-gE antibody cut-off value for seropositivity (97 mIU/mL), for participants who are seronegative at pre-vaccination.

CCI

Seropositivity is defined as the percentage of participants whose concentration is greater than or equal to the assay cut-off value (97 mIU/mL).

**Table G: Assay Derivation Rules**

IS.ISORRES	Derived value
“NEG”, “-”, or “(-)”	assay cut-off/2
“POS”, “+”, or “(+)”	assay cut-off
“< value” and value is $\leq$ assay cut-off	assay cut-off/2
“< value” and value is $>$ assay cut-off	Value
“> value” and value is $<$ assay cut-off	assay cut-off/2
“> value” and value is $\geq$ assay cut-off	Value
“value” and value is $<$ assay cut-off	assay cut-off/2
“value” and value is $\geq$ assay cut-off	Value
“value” and value is $>$ ULOQ	ULOQ
All other cases	Missing

Note: The Reverse Cumulative Distribution curves (RCC) generated will not use the ULOQ/LLOQ values but the exact value if the exact value is greater than ULOQ or below the LLOQ.

[figure not shown]
Numerical serology results will be derived from the content of IS.ISORRES in the SDTM dataset. For all the assays available for the study, assay derivation rules are included in [Table G](#).

LLOQ value for anti-gE antibody concentrations, and LLOQ and ULOQ values for RSV-A and RSV-B titers and concentrations are as per APPENDIX 3 of this SAP.

## 6.7. Software Version

All analyses will be conducted using SAS version 9.4 or above.

CCI

## 7. STATISTICAL CONSIDERATIONS

### 7.1. Adjustments for Covariates and Factors to be Included in Analyses

The following factors will be used in the ANCOVA analyses: age group at vaccination (50 to 59, 60 to 69 or  $\geq 70$  YOA) and study intervention group (Co-Ad or Control). The following covariate will be used in the ANCOVA: pre-dose  $\log_{10}$ -transformed concentration/titer. For details, refer to [15.1](#) and [15.2](#).

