### **6.3.3 Intervention Allocation to the Participant**

Approximately 530 eligible participants will be randomly (1:1) assigned to 2 study groups using a centralized randomization system on internet at Visit 1 (Day 1). The randomization algorithm will use a minimization procedure accounting for age (50 to 59, 60 to 69,  $\geq 70$  years) and center. Minimization factors will have equal weight in the minimization algorithm.

After obtaining the signed and dated Informed Consent Form (ICF) from the participant and if the participant is eligible, the delegated clinical trial staff will access IWRS. Upon entering the participant ID and age, the randomization system will determine the treatment group and provide the treatment number to be used for the trial intervention. The treatment number(s) to be used for subsequent dose administration(s) will be provided by the same IWRS.

Instructions related to instances when IWRS is not available will be provided to the site.

Refer to the IWRS user manual for additional information related to the treatment number allocation.

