### 9.3.1 Primary Endpoints/Estimands Analysis

The primary endpoints are described in [Section 3.0](#). The confirmatory analyses of non-inferiority will be based on the Per-Protocol set (PPS).

- Method for non-inferiority of the HZ/su vaccine in terms of enzyme linked immunosorbent assay (ELISA) Ab GMC between group ratio for gE at 1-month after the second HZ/su vaccination (i.e., at Day 91 for both Co-ad and Control groups):  
The least square point estimate and its 2-sided 95% CI for Group GMC ratio between the Control group over Co-ad group will be derived from an ANCOVA model\* on  $\log_{10}$  transformed concentrations.
- Method for non-inferiority of RSV investigational vaccine in terms of RSV-A neutralizing GMT between group ratio at 1-month after the RSVPreF3 OA investigational vaccine dose (i.e., at Day 31 for Co-ad group, and at Day 61 for Control group):  
The least square point estimate and its 2-sided 95% CI for Group GMT ratio between Control group over Co-ad group will be derived from an ANCOVA model\* on  $\log_{10}$  transformed titer.
- Method for non-inferiority of RSV investigational vaccine in terms of RSV-B neutralizing GMT between group ratio at 1-month after the RSVPreF3 OA investigational vaccine dose (i.e., at Day 31 for Co-ad group, and at Day 61 for Control group):

The least square point estimate and its 2-sided 95% CI for Group GMT ratio between Control group over Co-ad group will be derived from an ANCOVA model\* on  $\log_{10}$  transformed titer.

*\*The model will include the treatment group and the age category (age at vaccination: 50 to 59, 60 to 69, or  $\geq 70$ ) as fixed effects, and the pre-vaccination  $\log_{10}$ -transformed titer as covariate. Missing data will not be replaced. Titers below the assay cut-off will be replaced by half the assay cut-off; titers above the upper limit of quantification (ULOQ) will be replaced by the ULOQ.*

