## 2.4. Estimands

The primary, and secondary estimands to support regulatory decisions are described in the following table:

	Study Intervention	Population	Variable (or endpoint)	Intercurrent events (ICEs)		Population level summary
				Description	Handling strategy	
Primary	RSVPreF3 OA (one dose) and HZ/su (two doses) co-administered (Co-Ad) or received separately (Control)	Adults aged $\geq$ 50 years of age (YOA)	GMCs for anti-gE antibody (Ab) concentrations.	1. Permanently discontinued from study due to any reasons prior to 30 days after vaccine administration (Visit 4 for Co-Ad group and Control group) 2. Study intervention not administered per protocol 3. Prohibited medication or intercurrent medical condition prior to Visit 4 blood sampling 4. HZ/su vaccine doses or blood samples for anti-gE antibody concentrations (for baseline or testing) taken out of window	1. Missing data won't be imputed. Summaries will present the actual data. 2. Participant excluded from the immunogenicity analysis. 3. Participant excluded from the immunogenicity analysis. 4. Participant excluded from the immunogenicity analysis. 5. Participant excluded from the immunogenicity analysis.	The least square point estimate and its 2-sided 95% CI for between group GMC ratio derived from an ANCOVA model which includes the treatment group and the age category (age at vaccination: 50 to 59, 60 to 69, or $\geq$ 70) as fixed effects, and the pre-vaccination log10 transformed titer as covariate, in terms of enzyme linked immunosorbent assay (ELISA) antibody concentration for gE between the Control group over Co-Ad group at 1-month after the second HZ/su vaccination (i.e., at

				5. No pre / post-vaccine immunogenicity results for anti-gE antibody concentrations available		Day 91 for both Co-Ad and Control groups)

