**Table A: Overall Power to Demonstrate Primary Non-Inferiority Objectives: Assuming 225 Evaluable Subjects in Each Group**

Endpoint	Standard deviation of $\log_{10}$ concentration	Reference ratio	Non inferiority margin	Type II error	Power
HZ/su vaccine Non-inferiority* (1-sided test with alpha=2.5%)					
GMCs Anti-gE ELISA Ab	0.35	1.05	1.5	0.3%	99.7%
RSVPreF3 OA investigational vaccine Non-inferiority* (1-sided test with alpha = 2.5%)					
GMTs RSV-A neutralizing titer	0.45	1.05	1.5	4.6%	95.4%
GMTs RSV-B neutralizing titer	0.45	1.05	1.5	4.6%	95.4%
Global Power and Global Type II error				9.5%	90.5%

Abbreviations: Ab=antibody; ELISA=enzyme linked immunosorbent assay; gE=varicella zoster virus -glycoprotein

CCI

E; GMC=geometric mean concentration; GMT=geometric mean titer; HZ/su=herpes zoster/subunit; RSV-A=respiratory syncytial virus subtype A; RSV-B=respiratory syncytial virus subtype B.

\*Pass 2019 alpha = 2.5%, Two-Sample T-Tests for Non-Inferiority Assuming Equal Variance and Equal mean, Power = 100-the Type II error (Beta). The Global Type II error (Beta) has been adjusted using Bonferroni's method (Global Type II error = sum of the individual Type II errors).

For RSVPreF3 OA investigational vaccine: non-inferiority limit = 1.5 ( $\log_{10}[1.5] = 0.176$ )

For HZ/su vaccine: non-inferiority limit = 1.5 ( $\log_{10}[1.5] = 0.176$ )

Reference Ratio= 1.05 ( $\log_{10}[1.05] = 0.021$ )

Considering a slight interference of 1.05 for the reference ratio in favor of the control group versus Co-Ad group with a common population standard deviation of 0.45 for the  $\log_{10}$  transformed RSV-A/RSV-B neutralizing titer and 0.35 for the  $\log_{10}$  transformed HZ/su anti-gE Ab GMC, the study has at least 90.5% power to meet the primary objectives.

[figure not shown]

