**Figure A: Study Schema**

Abbreviations: AE=Adverse Event; Co-Ad group=Co-Administration group; D=Day; Hz/su=herpes zoster recombinant subunit; GSK=GlaxoSmithKline; N=Number of participants; pIMD=potential Immune-Mediated Disease; RSV=RSVPreF3 OA investigational vaccine; SAE=Serious Adverse Event.

Medically stable older adults  $\geq 50$  YOA will be enrolled in this study according the inclusion and exclusion criteria (see protocol Section 5.0). Approximately 530 participants will be randomly assigned to the 2 study intervention groups in a 1:1 ratio prior to intervention to provide approximately 265 enrolled participants in each study intervention group.

The randomization algorithm will use a minimization procedure accounting for age (50-59, 60-69, or  $\geq 70$  years) and center. Minimization factors will have equal weight in the minimization algorithm. Participants will be enrolled in 3 age categories with a balance between males and females. It is intended to enroll:

- Approximately 30% of participants 50 to 59 YOA, approximately 30% of participants 60 to 69 YOA, and approximately 25% of participants  $\geq 70$  YOA. The remaining 15% will be distributed freely across the three age categories.
- Approximately 40% of participants from each sex. The remaining 20% can be distributed freely between the 2 sexes.

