### 7.2. Multicenter Studies

This study will be conducted by multiple investigators in multiple countries. The participants will be randomized to one of the 2 groups (refer to [Table B](#) in section 3.1) which will be performed in a 1:1 ratio prior to intervention to provide approximately 265 enrolled participants per study intervention group.

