#### **15.1.4. Analysis for Primary Immunogenicity Variables**

Sensitivity analysis will be performed on the primary immunogenicity endpoints using the same primary ANCOVA model with the treatment group and age category (age at vaccination: 50-59, 60-69 or  $\geq 70$  years) as fixed effects and the pre-vaccination log10-transformed concentration or titer as applicable, as regressors, and with the addition of center as a random effect.

A second sensitivity analysis for the primary immunogenicity endpoints for RSV-A/B will be performed as described in Section 15.1.3. on a modified PPS including participants who received only one dose of HZ/su vaccine in the Co-Ad group.

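### Center is a minimization factor but is left out of the primary ANCOVA, so the three deciding confidence intervals are somewhat too wide if centers differ

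*SAP*

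**What the plan says.** **Allocation.** Protocol 4.1 and 6.3.3 describe 1:1 allocation by minimization on age category "and center. Minimization factors will have equal weight in the minimization algorithm". SAP 3.1 repeats it: "The randomization algorithm will use a minimization procedure accounting for age", again with center as the second factor.

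**Primary model.** Protocol 9.3.1 states that "The model will include the treatment group and the age category" as fixed effects, plus the pre-vaccination log10 value. The SAP 2.4 estimand table gives estimates "derived from an ANCOVA model which includes the treatment group and the age category". SAP 7.1 lists the same terms ("The following factors will be used in the ANCOVA analyses: age group at vaccination", then study group, then the pre-dose covariate), and SAP 15.1.3 applies the model to anti-gE, RSV-A and RSV-B. None of these includes center.

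**Where center appears.** SAP 15.1.4 specifies a sensitivity analysis of the primary endpoints using the same model "and with the addition of center as a random effect". SAP 7.2, on multicenter studies, says "This study will be conducted by multiple investigators in multiple countries" and restates the randomization ratio. It does not say how center is handled or why the primary model omits it.

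**Decision rule.** Under Protocol 9.3.1.1 and SAP 7.4 and 15.1.3, success depends on the upper limit of the two-sided 95% CI being at most 1.5. SAP 15.1.3 attaches this rule to the model without center.

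**The concern.** Minimization makes the arms more alike on center than simple randomization would. If mean responses differ between centers after adjustment for age and baseline, the treatment estimate is correspondingly more precise. A model without center does not see this: the between-center variation stays in its residual, and it reports a standard error that is too large.

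The three intervals that decide the trial therefore ignore one of the two factors used for allocation. What is at stake is attainable precision. A false non-inferiority claim does not become more likely.

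**Working it through.** **Inputs from the documents.** 225 evaluable per group; SD of log10 values 0.45 (RSV-A, RSV-B) and 0.35 (anti-gE); margin 1.5; assumed true ratio 1.05; one-sided alpha 2.5%; 15% not evaluable (Protocol 9.1 and 9.5, Table 19; SAP 2.5, Table A). The method is given as "Two-Sample T-Tests for Non-Inferiority Assuming Equal Variance and Equal mean".

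**Input that must be assumed.** ICC, the share of residual variance lying between centers after age and baseline. The documents give no value, so a range is shown.

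**1. The plan's own power.** With delta = log10(1.5) − log10(1.05) = 0.155 and 448 degrees of freedom, the non-central t gives 99.68% for anti-gE (stated 99.7%) and 95.38% for each RSV endpoint (stated 95.4%). Summing the type II errors, 100 − 0.32 − 4.62 − 4.62 = 90.44%; the stated 90.5% comes from the rounded errors 0.3 + 4.6 + 4.6 = 9.5%. Also 225/0.85 = 265 per group. The figures reproduce. They use the total SD with no covariates, so leaving center out does not undermine them.

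**2. Exact within-center balance.** The model without center reports SE = SD × √(2/n), while the true SE is SD × √((1 − ICC) × 2/n). Hence:

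- excess CI width on the log scale = 1/√(1 − ICC) − 1
- actual one-sided type I error = P(Z > 1.96/√(1 − ICC))
- largest observed ratio that still passes = 1.5 / 10^(t × SE), with t = 1.965

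For RSV without center, SE = 0.45 × √(2/225) = 0.0424 and the CI factor is 10^(1.965 × 0.0424) = 1.212, so the largest passing ratio is 1.5/1.212 = 1.238. This takes no credit for the baseline covariate.

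| ICC | Excess CI width | Type I error, no center | Largest passing RSV ratio, center modelled | RSV power, without / with center |
|---|---|---|---|---|
| 0 | 0% | 2.5% | 1.238 | 95.4% / 95.4% |
| 0.02 | 1.0% | 2.4% | 1.240 | 95.6% / 95.8% |
| 0.05 | 2.6% | 2.2% | 1.244 | 95.8% / 96.3% |
| 0.10 | 5.4% | 1.9% | 1.250 | 96.2% / 97.0% |

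Anti-gE power changes by less than 0.1 point.

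**3. Imperfect balance.** This was simulated with 530 randomized, equal-weight minimization on three age groups and center, 15 or 40 unequal centers, 15% random loss to the per-protocol set and a true ratio of 1.5. The ANCOVA was compared with a REML random-center model over 20,000 runs per setting (Monte Carlo SE about 0.11 points). The number of centers, an assignment probability of 0.8 and a baseline correlation of 0.5 are assumptions.

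| ICC | CI without center wider by | Type I error without center |
|---|---|---|
| 0 | 0.2–0.3% | 2.5–2.6% |
| 0.02 | 0.9% | 2.4–2.5% |
| 0.05 | 2.0–2.2% | 2.3–2.4% |
| 0.10 | 4.5–4.7% | 2.1% |

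With center modelled, type I error stays at 2.4–2.6% throughout. A separate simulation with fixed center effects and 15 centers gives width ratios of 0.997, 1.021 and 1.047 at ICC 0, 0.05 and 0.10, in line with the table except that at ICC 0 the fixed center terms cost slightly more than they gain.

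**The case against.** The strongest reply is that the plan already contains the model being asked for. SAP 15.1.4 specifies it, SAP 7.1 refers the reader to section 15.1, and both results will be reported. On this view only the label is in dispute, and the present choice is valid and slightly conservative. It costs nothing against plan: the global power of the primary ANCOVA is 93.5% or 97.5% at an assumed baseline correlation of 0.3 or 0.5, above the stated 90.5%. Since SAP Appendix 1 prints ratios to two decimals, the passing thresholds 1.238, 1.240 and 1.244 all appear as 1.24.

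The effect may also be very small. Serology is run blinded by the sponsor's laboratory or its delegate, and baseline is in the model, so residual center differences could be slight. The RSV per-protocol criteria differ by arm (SAP 5.5), which makes within-center balance in that set less certain than random loss implies.

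Finally, a change is more than editing. Protocol 9.3 called for a final SAP before the first visit, the current SAP is version 3.0 of 23 July 2024, the trial is open-label, and a mixed model needs a stated degrees-of-freedom method.

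The points on size and uncertainty stand, and they are why the concern is minor. The first point does not remove it: the sensitivity result has no role in deciding success, and the plan does not say what follows if the two models fall on opposite sides of 1.5. The degrees-of-freedom method has to be settled for SAP 15.1.4 in any case. The timing point limits when the swap can be made, not whether it is sound.

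**Conclusion.** The concern holds and is minor. The primary ANCOVA omits one of the two allocation factors, without explanation, in the three analyses that decide the trial. If the residual ICC lies between 0.02 and 0.10, the intervals are about 1% to 5% wider on the log scale than they need be, and the one-sided type I error falls to between 2.4% and 1.9% under exact balance. If centers do not differ, there is essentially no effect.

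The direction is conservative: no false non-inferiority claim is made more likely, and the stated 90.5% power is unaffected. The existence and direction of the effect follow from the design whenever centers differ. Its size rests on the assumed ICC and, in the simulations, on the assumed number of centers, assignment probability, baseline correlation and random loss.

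**What to change.** Make the SAP 15.1.4 model (treatment, age category in three strata, baseline log10 value, center as random effect) the primary analysis for all three endpoints, and keep the model without center as the sensitivity analysis. Add:

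- a fallback: if the center variance is estimated at zero, the result is that of the present ANCOVA;
- a rule for pooling centers with very few per-protocol participants;
- the degrees-of-freedom method.

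Align Protocol 9.3.1, the SAP 2.4 estimand table, and SAP 7.1, 7.2, 15.1.3 and 15.1.4. Record the change in SAP 3.3 if the SAP departs from the protocol. Confirm in SAP 15.2.3 that the RSV concentration ratios, which refer back to the primary model, are meant to follow it.

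No new data are needed, because two specified analyses exchange roles. The cost is the text changes and the added rules, which must be fixed before database lock and without sight of results by arm. With many sparse centers the variance may be estimated at zero and the gain nil. If the change can no longer be made in time, SAP 7.2 should at least say that center is omitted from the primary model, that this is conservative, and that SAP 15.1.4 examines it.

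Separately, as an erratum with no bearing on the above, SAP 15.1.3 prints the first age stratum as 50 to 69. It should read 50 to 59, as in Protocol 9.3.1 and SAP 2.4, 7.1 and 15.1.4.

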### 7.2. Multicenter Studies

This study will be conducted by multiple investigators in multiple countries. The participants will be randomized to one of the 2 groups (refer to [Table B](#) in section 3.1) which will be performed in a 1:1 ratio prior to intervention to provide approximately 265 enrolled participants per study intervention group.

